## **Appendix 7. Pregnancy Precautions, Definition for Female of Childbearing Potential, and Contraceptive Requirements**

The administration of filgotinib in embryofetal animal development studies resulted in decreased numbers of viable rat fetuses, increased resorptions, and visceral and skeletal malformations. Similar effects were noted in the rabbit. A safety margin relative to human exposure has not been identified. Pregnancy is contraindicated during use of filgotinib.

For participation in this study, the use of *highly effective* contraception is required as outlined below for all subjects who are of childbearing potential. In addition, during the study women of childbearing potential must have at minimum, a urine pregnancy test every 4 weeks.

### **1) Definitions**

#### **a. Definition of Childbearing Potential**

For the purposes of this study, a female-born subject is considered of childbearing potential following the initiation of puberty (Tanner stage 2) until becoming post-menopausal, unless permanently sterile or with medically documented ovarian failure. Women who do not meet below criteria for being post-menopausal, are not permanently sterile, or do not have medically documented ovarian failure must have pregnancy testing as outlined by the protocol.

Women are considered to be in a postmenopausal state when they are  $\geq 54$  years of age with cessation of previously occurring menses for  $\geq 12$  months without an alternative cause.

Permanent sterilization includes hysterectomy, bilateral oophorectomy, or bilateral salpingectomy in a female subject of any age. Bilateral tubal ligation is not considered permanent sterilization.

#### **b. Definition of Male Fertility**

For the purposes of this study, a male-born subject is considered fertile after the initiation of puberty unless permanently sterilized by bilateral orchidectomy or has medical documentation of permanent male infertility. Vasectomy is not considered permanent sterilization.

### **2) Contraception for Female Subjects**

#### **a. Study Drug Effects on Pregnancy and Hormonal Contraception**

Filgotinib is contraindicated in pregnancy as there is a possibility of human teratogenicity/fetotoxicity in early pregnancy based on non-clinical data. Data from a drug-drug interaction study of filgotinib and hormonal contraceptives (GS-US-417-3916) have demonstrated coadministration with filgotinib did not alter the pharmacokinetics of representative hormonal contraceptives, levonorgestrel/ethinyl estradiol.

For female subjects, hormonal contraceptives will be permitted as a form of contraception when used in conjunction with a barrier method (preferably a male condom). For male subjects, male condom should be used; for their female partners of childbearing potential, an accepted contraceptive method should also be considered. Details are outlined below.

Please refer to the latest version of the filgotinib IB for additional information.

#### **b. Contraception for Female Subjects of Childbearing Potential**

The inclusion of female subjects of childbearing potential requires the use of highly effective contraceptive measures. Women must have a negative serum pregnancy test at screening and a negative urine pregnancy test on the Day 1 visit prior to randomization. Pregnancy tests will be performed at monthly intervals thereafter. In the event of a delayed menstrual period (> one month between menstruations), a pregnancy test must be performed to rule out pregnancy. This is true even for women of childbearing potential with infrequent or irregular periods.

Female subjects must agree to use one of the following methods from screening until 35 days following the last dose of study drug.

- Complete abstinence from intercourse of reproductive potential. Abstinence is an acceptable method of contraception only when it is in line with the subject's preferred and usual lifestyle.

Or

- Consistent and correct use of 1 of the following methods of birth control listed below.
  - Intrauterine device (IUD) with a failure rate of < 1% per year
  - Tubal sterilization
  - Essure micro-insert system (provided confirmation of success 3 months after procedure)
  - Vasectomy in the male partner (provided that the partner is the sole sexual partner and had confirmation of surgical success 3 months after procedure)

Female subjects, who wish to use a hormonally based method, must use it in conjunction with a barrier method; the barrier method is to be used either by the female subject or by her male partner. Female subjects who utilize a hormonal contraceptive as one of their birth control methods must have consistently used the same method for at least three months prior to study dosing. Hormonally-based contraceptives and barrier methods permitted for use in this protocol are as follows:

- Hormonal methods (each method *must* be used with a barrier method, preferably male condom )
  - Oral contraceptives (either combined estrogen/progestin or progesterone only)
  - Injectable progesterone
  - Implants of levonorgestrel
  - Transdermal contraceptive patch
  - Contraceptive vaginal ring
- Barrier methods (each method *must* be used with a hormonal method)
  - Male or female condom with or without spermicide
  - Diaphragm with spermicide
  - Cervical cap with spermicide
  - Sponge with spermicide

All female subjects must also refrain from egg donation and in vitro fertilization during treatment and until at least 35 days after the last study drug dose.

### **3) Contraception Requirements for Male Subjects**

It is theoretically possible that a relevant concentration of study drug may be achieved in a female partner from exposure to the male subject's seminal fluid. Therefore, male subjects with female partners of childbearing potential must use condoms during study participation and for 90 days after the last study drug dose. Female partners of male study subjects should consider using one of the above methods of contraception as well. Male subjects must also refrain from sperm donation during treatment and until at least 90 days after the end of study drug dosing.

#### **4) Unacceptable Birth Control Methods**

Birth control methods that are unacceptable include periodic abstinence (eg, calendar, ovulation, symptothermal, post-ovulation methods), withdrawal (coitus interruptus), spermicides only, and lactational amenorrhea method (LAM). Female condom and male condom should not be used together.

#### **5) Procedures to be Followed in the Event of Pregnancy**

Subjects will be instructed to notify the investigator if they become pregnant at any time during the study, or if they become pregnant within 30 days of last study drug dose. Subjects who become pregnant or who suspect that they are pregnant during the study must report the information to the investigator and discontinue study drug immediately. Subjects whose partner has become pregnant or suspects she is pregnant during the study are to report the information to the investigator.

Instructions for reporting pregnancy, partner pregnancy, and pregnancy outcome are outlined in Section [7.7.2.1](#).

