## **7.7.2. Instructions for Reporting Special Situations**

### **7.7.2.1. Instructions for Reporting Pregnancies**

The investigator should report pregnancies in female study subjects that are identified after initiation of study drug and throughout the study, including the post study drug follow-up period, to DIVERSITY\[contact] using the pregnancy report form within 24 hours of becoming aware of the pregnancy.

Refer to Section 7.3 and the eCRF completion guidelines for full instructions on the mechanism of pregnancy reporting.

The pregnancy itself is not considered an AE nor is an induced elective abortion to terminate a pregnancy without medical reasons.

Any premature termination of pregnancy (eg, a spontaneous abortion, an induced therapeutic abortion due to complications or other medical reasons) must be reported within 24 hours as an SAE. The underlying medical reason for this procedure should be recorded as the AE term.

A spontaneous abortion is always considered to be an SAE and will be reported as described in Section 7.3. Furthermore, any SAE occurring as an adverse pregnancy outcome post study must be reported to DIVERSITY\[contact].

The subject should receive appropriate monitoring and care until the conclusion of the pregnancy. The outcome should be reported to DIVERSITY\[contact] using the pregnancy outcome report form. If the end of the pregnancy occurs after the study has been completed, the outcome should be reported directly to DIVERSITY\[contact].

Pregnancies of female partners of male study subjects exposed to the Sponsor's or other study drugs must also be reported and relevant information should be submitted to DIVERSITY\[contact] using the pregnancy and pregnancy outcome forms within 24 hours. Monitoring of the subject should continue until the conclusion of the pregnancy. If the end of the pregnancy occurs after the study has been completed, the outcome should be reported directly to DIVERSITY\[contact].

Refer to Appendix 7 for Pregnancy Precautions, Definition for Female of Childbearing Potential, and Contraceptive Requirements.

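### Pregnancy notification in Appendix 7 stops at day 30 for women and has no post-dose period for men's partners, short of the protocol's own 35- and 90-day contraception periods

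*Protocol*

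**What the plan says.** All the windows are in the protocol.

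- **Women, contraception.** Appendix 7, item 2b, requires it "from screening until 35 days following the last dose of study drug". The egg-donation and IVF restriction in Appendix 7 and the exclusion criteria in Sections 4.2.2 and 4.5.2 use the same 35 days.
- **Women, notification.** Appendix 7, item 5, covers pregnancies during the study or "if they become pregnant within 30 days of last study drug dose".
- **Men, contraception.** Appendix 7, item 3, says men with partners of childbearing potential "must use condoms during study participation and for 90 days after the last study drug dose". The bar on sperm donation is also 90 days.
- **Men, notification.** Appendix 7, item 5: "Subjects whose partner has become pregnant or suspects she is pregnant during the study are to report the information to the investigator". No post-dose period is given.
- **Investigator's duty.** Section 7.7.2.1 has female subjects' pregnancies reported when identified after drug start and "throughout the study, including the post study drug follow-up period". For partners of men exposed to the sponsor's "or other study drugs must also be reported and relevant information should be submitted to" the safety mailbox within 24 hours, with no end date. It adds that "any SAE occurring as an adverse pregnancy outcome post study must be reported".
- **Follow-up.** Section 6.5 places the post-treatment visit, which includes a pregnancy test, 30 days after the last dose. Subjects who enter the extension study skip it.

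**The concern.** The sponsor set 35 and 90 days as the periods in which conception should be avoided and repeated them in several places. The instruction on what subjects should tell the site uses neither figure, and the protocol gives no reason for the difference. A site and subject following the text exactly could leave a pregnancy that arose inside a precaution window unknown to the investigator.

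For women, Section 1.4 reports embryofetal malformations in animals at exposures similar to or slightly above those at 200 mg daily, and Appendix 7 says no safety margin relative to human exposure has been identified. For partners the basis is weaker: "It is theoretically possible that a relevant concentration of study drug may be achieved in a female partner" through seminal fluid.

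The potential loss is limited. Adverse outcomes that are SAEs remain reportable after the study once known. What may be missed is awareness of the pregnancy itself, and with it the pregnancies that end normally. Awareness comes first, because Section 7.3.2 does not oblige investigators to look for SAEs after follow-up has ended.

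**Working it through.** No sample size, power or alpha is involved, and the plan states no figure to reproduce. The check compares windows, in days after the last dose.

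| | Contraception ends | Notification ends |
|---|---|---|
| Female subjects | 35 (App. 7, item 2b) | 30 (App. 7, item 5) |
| Partners of male subjects | 90 (App. 7, item 3) | end of the study, no day given (App. 7, item 5) |

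Gap = contraception window − notification window.

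**Reading 1: the study ends for a subject at the 30-day post-treatment visit.**
- Women: 35 − 30 = 5 days (days 31–35).
- Partners: 90 − 30 = 60 days (days 31–90).

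**Reading 2: the study ends for a subject at the last dose.**
- Women: unchanged at 5 days, because item 5 gives them 30 days explicitly.
- Partners: 90 − 0 = 90 days.

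**Reading 3: the study means the trial-level End of Study in Section 3.7**, when the last subject has finished treatment plus 30 days. Let D be the days from this subject's last dose to the last subject's last dose. Trial end then falls D + 30 days after this subject's last dose.
- Women: max(0, 35 − (D + 30)) = max(0, 5 − D).
- Partners: max(0, 90 − (D + 30)) = max(0, 60 − D).
- At D = 0 the gaps are 5 and 60 days. At D = 5 the women's gap is 0. At D ≥ 60 both are 0.

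Reading 3 would make the separate 30-day clause for women redundant, since trial end is never earlier than 30 days after a subject's last dose. Reading 1 is therefore the more natural.

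**Does Section 7.7.2.1 close the gap?**
- *Women.* The duty runs to the end of post-drug follow-up, which is day 30 under Section 6.5. No planned contact or test falls in days 31–35. The two texts also use different triggers: Section 7.7.2.1 goes by when the pregnancy is identified, Appendix 7 by when it arose. A conception before day 30 that is recognised later is therefore treated differently by the two.
- *Partners.* The duty has no end date, but the investigator can report only what the site learns. With no visit after day 30, that depends on the subject.

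**Who is affected?** Subjects who stop drug and do not enter the extension study: those who opt out (Section 3.2), those who withdraw (Section 3.5.2), and those whose worsening requires prohibited medication or surgery and who do not qualify (Section 3.6).

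**With the proposed change:** 35 − 35 = 0 and 90 − 90 = 0.

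**The case against.** Contraception and notification serve different purposes, and nothing in the documents says their periods must match. Thirty days is the protocol's general safety window: AEs are collected for 30 days after the last dose (Section 7.3.1) and the final visit is at day 30. This explains where the 30 days may have come from. It does not explain why conceptions inside the sponsor's own precaution period should fall outside notification.

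The partner sentence can also be read with its study limit attached only to a suspected pregnancy, leaving a confirmed one without an end date, as in Section 7.7.2.1. That reading is possible. It means the 60 days rests on one reading of an unclear instruction, and the same edit removes the ambiguity.

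Drug exposure on days 31–35 is not supported by the documents. The elimination data in Section 1.2.2.3 are nonclinical: half-lives of 4 and 5 hours in rat and dog, with excretion nearly complete within 24 and 48 hours respectively. No human half-life is given. The animal malformations relate to exposure during dosing. This stands and keeps the point minor.

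The consent pages were not available for this review, and Section 7.7.2.1 defers to eCRF guidelines that are not in these documents. Either may already give subjects or sites longer periods. That cannot be checked here.

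Finally, an amendment needs ethics approval (Sections 9.1.2 and 9.2.1) across about 500 planned sites. That is a real cost, though an administrative one.

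**Conclusion.** The concern holds as a minor safety-reporting point. On the more natural reading, notification falls short of contraception by 5 days for women and 60 days for partners of male subjects. On the trial-level reading the gaps are 0–5 and 0–60 days, depending on when the subject stopped relative to the last subject. Section 7.7.2.1 narrows the partner side by leaving the investigator's duty open-ended, but closes neither gap.

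The conclusion assumes that the protocol text is what subjects are told, and it applies only to those who do not enter the extension study. Some pregnancies may go unreported; the documents do not allow an estimate of how many. No endpoint or efficacy analysis is affected.

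**What to change.** In Appendix 7, item 5, ask female subjects to notify the investigator of any pregnancy arising during the study or up to 35 days after the last dose. Ask male subjects to notify of any partner pregnancy arising during the study or up to 90 days after the last dose. In Section 7.7.2.1, state the same two periods as minimums, counted by the date the pregnancy arose and applying whenever it is identified. Leave the existing rule on post-study SAE outcomes as it is.

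The cost is wording in two places, any matching change to subject materials, and the usual ethics submission. No visit, test or procedure is added.

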#### **Pregnancy Testing**

All females of childbearing potential will have urine pregnancy testing every 4 weeks (in clinic) during their study participation. If a urine pregnancy test is positive, the subject should stop study drug immediately, contact the investigator, and have confirmatory serum pregnancy test in clinic.

**Appendix 8. Clinical Laboratory Assessment Table**

Hematology	Chemistry	Urinalysis	Other
Hematocrit Hemoglobin Platelet count Red blood cell (RBC) count White blood cell (WBC) count Differentials (absolute and percentage), including: Lymphocytes Monocytes Neutrophils Eosinophils Basophils Reticulocyte count Mean corpuscular volume (MCV)	Alkaline phosphatase Aspartate aminotransferase (AST) Alanine aminotransferase (ALT) Total bilirubin Direct and indirect bilirubin Total protein Albumin Bicarbonate Blood urea nitrogen (BUN) Calcium Chloride Serum creatinine Creatinine clearance CC&G Glucose Phosphorus Magnesium Potassium Sodium Creatine Phosphokinase (CPK)	Appearance: Blood Color Glucose Leukocyte esterase pH Protein Urobilinogen	Urine drug screen for: Amphetamines Cocaine Barbiturates Opiates Benzodiazepines CCI * Leukocyte subsets* CCI QuantiFERON® TB – Gold In-Tube Analysis (if required per inclusion criteria) RNA Biopsy (histology) CCI Bacterial stool culture C-Diff Toxin Ova and Parasites (O&P) CCI CCI Pharmacokinetics (PK) Serum immunoglobulin Prothrombin Time (PT) Partial thromboplastin time (PTT) International Normalized Ratio (INR)
		Serology	
		Hepatitis B surface antigen (HBsAg) Hepatitis B surface Ab (HBsAb) Hepatitis B core Ab (HBcAb) HBV DNA Hepatitis C Ab HCV RNA HIV	
		Pregnancy	
		In females of childbearing potential: Serum pregnancy Urine pregnancy	
		Fasting lipids	
		Triglycerides Cholesterol and its subfractions (high-density lipoprotein [HDL] and low density lipoprotein [LDL])	

\* CCI and Leukocyte subsets in North America only

## LIST OF ABBREVIATIONS

6-MP	6-mercaptopurine
AE	adverse event
AEI	adverse event of interest
ALT	alanine aminotransferase
ANCOVA	analysis of covariance
AST	aspartate aminotransferase
ASTE	arterial systemic thromboembolism
BLQ	below the limit of quantitation
BMI	body mass index
CD	Crohn's disease
CDAI	Crohn's Disease Activity Index
CI	confidence interval
CMH	Cochran-Mantel-Haenszel
COVID-19	coronavirus disease 2019
CCI	[REDACTED]
CSR	clinical study report
CTCAE	Common Terminology Criteria for Adverse Events
DMC	data monitoring committee
ECG	electrocardiogram
eCRF	electronic case report form(s)
CCI	[REDACTED]
CCI	[REDACTED]
ET	early termination
EU	European Union
FAS	Full Analysis Set
FWER	family-wise type I error rate
CCI	[REDACTED]
Gilead	Gilead Sciences
CCI	[REDACTED]
HDL	high-density lipoprotein
HLGT	high-level group term
HLT	high-level term
CCI	[REDACTED]
CCI	[REDACTED]
IBD	inflammatory bowel disease
CCI	[REDACTED]
ID	identification
Ig	immunoglobulin

IWRS	interactive web response system
LDL	low-density lipoprotein
LLOQ	lower limit of quantitation
LLT	lower-level term
LOCF	last observation carried forward
LOQ	limit of quantitation
LS	least squares
LTE	long-term extension
MACE	major adverse cardiovascular events
M-Day	maintenance study day
MedDRA	Medical Dictionary for Regulatory Activities
MH	Mantel-Haenszel
MI	myocardial infarction
MICE	multivariate imputation by chained equations
CCI	[REDACTED]
MST	MedDRA search term
MTX	methotrexate
NCEP	National Cholesterol Education Program
NLP	natural language processing
CCI	[REDACTED]
PGIC	Patient Global Impression Change
PGIS	Patient Global Impression Severity
PK	pharmacokinetic
PKAP	Pharmacokinetic analysis plan
PRO2	patient reported outcome consisting of 2 items: abdominal pain severity and liquid stool frequency
PT	preferred term
PTM	placebo-to-match
Q1	first quartile
Q3	third quartile
CCI	[REDACTED]
SAE	serious adverse event
SAP	statistical analysis plan
SD	standard deviation
SE	standard error
SES-CD	Simple Endoscopic Score for Crohn's Disease
CCI	[REDACTED]
SMQ	Standardised MedDRA Query
SOC	system organ class
T-Day	subject activation date on the electronic diary device during screening

TEAE	treatment-emergent adverse event
TFLs	tables, figures, and listings
TNF- $\alpha$	tumor necrosis factor-alpha
ULN	upper limit of normal
US	United States
V-Day	visit day
VAS	visual analogue scale
VTE	venous thromboembolism
WHO	World Health Organization

**CCI**

### PHARMACOKINETIC ABBREVIATIONS

AUC	area under the concentration versus time curve
AUC tau	area under the concentration versus time curve over the dosing interval
C max	the maximum observed concentration of drug in plasma
CL ss /F	apparent oral clearance at steady state
C tau	observed drug concentration at the end of the dosing interval
T max	the time (observed time point) of C max

## 1. INTRODUCTION

This statistical analysis plan (SAP) describes all statistical analyses methods required to address both the EU and non-EU specific objectives. It also describes all tables, figures, and listings (TFLs) to be included in the clinical study report (CSR) for Study Protocol GS-US-419-3895/GLPG0634-CL-309.

This SAP is based on the study protocol Amendment 9 dated 02 December 2021 and the electronic case report forms (eCRF). The SAP will be approved before database finalization of the final analysis. Any changes made after the finalization of the SAP will be documented in the CSR.

### 1.1. Study Objectives

The overall objective of the study is to evaluate the effect of treatment with filgotinib on the induction and maintenance of clinical remission and endoscopic response in subjects with moderately to severely active Crohn's disease (CD). Subjects who are biologic-naive or biologic-experienced will be enrolled in Cohort A and subjects who are biologic-experienced will be enrolled in Cohort B, respectively. Treatment assignments will be randomized within each cohort.

#### 1.1.1. Primary Objectives

The primary objectives are:

##### Induction Studies (Cohorts A and B) (EU-specific)

- To evaluate the efficacy of filgotinib as compared to placebo in establishing clinical remission by Patient Reported Outcome (PRO2) at Week 10
- To evaluate the efficacy of filgotinib as compared to placebo in establishing endoscopic response at Week 10

##### Induction Studies (Cohorts A and B) (other: non-EU)

- To evaluate the efficacy of filgotinib as compared to placebo in establishing clinical remission by Crohn's Disease Activity Index (CDAI) at Week 10

To evaluate the efficacy of filgotinib as compared to placebo in establishing endoscopic response at Week 10

